It has been reported that the prevalence of malnutrition in cancer patients varies from 30% to 80% according to the different distribution characteristics of the enrolled population in different studies [8]. A systematic review from 2006 to 2017 found that the Physical function and nutritional status were the most predictive domains for mortality [9]. At the same time, MNA score is widely used in tumor research of all ages [10], and it has been proved that MNA nutritional assessment can simply and quickly evaluate the nutritional status of patients according to anthropometric values, basic activity ability and eating conditions, and form a relatively complete evaluation system combined with blood albumin and other values [11], The score is also used to evaluate the baseline nutritional status of a variety of tumors and has good prognostic value in clinical outcome [12]. In rectal cancer, head and neck cancer and even non solid tumors such as acute lymphoblastic leukemia, higher MNA score has been proved to be an independent risk factor of prognosis [13]. Regarding the close relationship between this evaluation method and multiple clinical complications and prognostic factors, in recent years, people have gradually realized that early screening of the nutritional status of tumor patients and further receiving an appropriate intervention are particularly important to improve the influences on the outcomes of tumors. The American Society of Clinical Oncology also recommended the routine application of MNA score in the basic evaluation of nutritional status of 65 year old patients receiving chemotherapy in 2020 [7]. However, the application of this scoring system in early and mid-term lung cancer is very limited, studies examining the clinical features and nutritional status of patients in early mid-term NSCLC are thus necessary.

Therefore, this study aims to observe the correlation between sarcopenia and the

prognosis of patients with early mid-term non-small cell lung cancer, clarify the value of sarcopenia and nutritional status in predicting the overall survival rate and progression-free survival rate of patients with non-small cell lung cancer, and explore the value of early screening and nutritional intervention in predicting the prognosis of patients with lung cancer, To provide evidence-based research for alleviating the social and economic burden of lung cancer patients.

2、Research purpose

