1. Identify the prevalence of sarcopenia in patients with early and mid-term non-small cell lung cancer as well as the anthropometry, clinical characteristics, tumor stage and treatment methods of this population, to compare and analyze the differences of clinical characteristics such as smoking status, tumor stage, EGFR gene expression, nutritional score and physical endurance with patients with non-small cell lung cancer.
2. Multivariate logistic analysis aim to explore the related risk factors of sarcopenia in patients with early and mid-term non-small cell lung cancer.
3. To clarify the impact of sarcopenia on the overall survival rate and progression-free survival rate of early and mid-term non-small cell lung cancer, and its clinical value as a predictor of the prognosis of patients.

3、Type of experimental design, grouping method

- 1) Study case collection scope: including respiratory ward, respiratory intensive care unit and respiratory outpatient department of Huadong Hospital Affiliated to Fudan University.
- 2) This study was a prospective, and observational cohort study. The follow-up results were grouped according to the diagnostic criteria of sarcopenia.

4、Case inclusion criteria and exclusion criteria

1. inclusion criteria

- (1) The patients with non-small cell lung cancer diagnosed by cytology or pathology meet the standards of clinical diagnosis and treatment guidelines for lung cancer of Chinese Medical Association (2018 Edition), and the TNM staging diagnosis of lung cancer meets the stage IA-IIIA.

(2) The medical records are complete.

2. exclusion criteria

- (1) Severe heart failure, acute progressive pulmonary inflammation ,acute liver and kidney dysfunction in recent 2 weeks;
- (2) Incomplete clinical and follow-up data or disagreement or inability to conduct regular follow -up CT imaging evaluation;
- (3) Patients with other malignant tumors and a history of related tumor chemotherapy within half year, previous history of radiotherapy;
- (4) Unable to stand or walk, unable to cooperate to complete the walking test, and patients with past unconscious fall history and fall risk;
- (5) Unable to complete BIA examination due to pacemaker implantation and other reasons;
- (6) Those who withdraw from the study for subjective reasons, regardless of the patient's loss of follow-up caused by any reason, shall be regarded as patients who withdraw from the study.

5、 Estimation of case sample size

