The diagnosis process of sarcopenia complies with the provisions of the Asian sarcopenia working group. The specific information collected for diagnosis includes: skeletal muscle mass of limbs: the skeletal muscle mass index (ASMI) is measured by Korea inbody570 (Korea Biospace) human composition analyzer. The decrease of skeletal muscle mass is defined as the decrease of male $< 7.0\text{kg}/\text{m}^2$ and female $< 5.7\text{kg}/\text{m}^2$; The Jamar hand dynamometer (USA) is used to measure the grip strength in the grip strength test. Patients are required to hold the grip strength tester in the dominant hand with standing position for 3 times, the maximum value were recorded. Male $< 28\text{kg}$ and female $< 18\text{kg}$ are defined as reduced grip strength; The time required for patients to walk at normal pace was measured by 6-meter distance pace measurement; If the walking speed is less than $0.8\text{m}/\text{s}$, it is defined as the decline of walking function; The decrease of ASMI accompanied by the decrease of grip strength or gait speed was diagnosed as sarcopenia.

5. Follow up endpoint

The primary endpoint was progression free survival (PFS) within 2 years, defined as the time from diagnosis to clinically recorded disease progression or death from any cause. The patients were followed up according to the outpatient and electronic medical records and telephone calls. The tumor treatment strategy and the time of clinical outcome or disease progression were followed up. The disease progression was defined as the 20% increase in sum of longest diameters from nadir (and a minimum absolute increase of 5 mm), or unequivocal increase in nontarget lesions according to RECIST solid tumor standard. The progress needs to be confirmed by at least one imaging and one clinical expert. The deadline for follow-up is 2 years. The secondary endpoint was overall survival time (OS), defined as

the outcome of patient death from diagnosis to any cause or the final follow-up time. During the follow-up, the researchers conducted disease evaluation, follow up of disease progress, grip strength test, walking test, muscle density measurement and nutritional score (MNA) at 6, 12, 18 and 24 months after enrollment. If feasible, the participants will continue to be followed up for up to five years.

7、Adverse events

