2. Analysis of risk factors of non-small cell lung cancer combined with sarcopenia: univariate and multivariate logistic analysis of relevant variables of patients with sarcopenia, including clinical data variables, nutritional status, tumor stage, serum C-reactive protein, cholesterol level, albumin level, EGFR gene expression, etc, Logistic regression was used to analyze the risk factors of sarcopenia in non-small cell lung cancer.
3. Prognostic value of sarcopenia in non-small cell lung cancer: progression free survival time PFS and overall survival time OS were statistically analyzed by Kaplan-Meier, and the difference was tested by log-rank method.

9、 Ethics related to experiment

The risk of patients participating in this study comes from the risk of tumor itself and tumor complications. It is an observational study without any intervention means such as drugs. The study itself does not increase the disease risk of patients. Patients can still stop treatment or withdraw from the study at any time, and subjects can stop the study at any time or for any reason at their own request or at the request of the investigator. For all subjects who withdrew from the study for any reason, contact themselves or their families or health care providers 24 weeks after withdrawal to determine the subject's life status. Subjects may voluntarily stop participating in the study at any time without affecting further treatment.

At the same time, ensure that after the end of the study and midway suspension, all participants continue to accept the disease medical measures recommended in the guidelines, do not change the follow-up further treatment, and do not intervene in the outcome of the disease.

10、 Recruitment methods and informed consent of subjects

This study used the recruitment method of clinical case collection, including respiratory ward, respiratory intensive care unit and respiratory clinic. All patients must

obtain informed consent and sign the informed consent form.

11、Expected progress and completion time of the study

Study period: October 15, 2021 to October 15, 2024

From October 2021 to November 2021, the research group collected personnel training and enrolled cases.

From November 2021 to November 2023, the case observation indexes, clinical data and follow-up data were collected.

From November 2023 to January 2024, the final follow-up was completed and the outcome events were collected and sorted out.

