From January 2024 to October 2024, statistics and data sorting, writing papers, accepting results and publishing articles.

12、Follow up and medical measures after the study

After the study, continue to accept the disease medical measures recommended by the guidelines, do not change the follow-up further treatment, and do not intervene in the outcome of the disease.

13、Responsibilities of each party and other relevant provisions

1. Research Division of labor: before the beginning of the research, the researchers shall be trained to be familiar with the research scheme and the principles of data collection. The researcher shall record the contents truthfully, in detail and carefully as required. The specific division of labor is as follows:

- [name], attending physician, research plan formulation, data collection and article writing
- [name], deputy chief physician, supervision and training of research program
- [name], resident patient follow-up and data management
- [name], attending physician, data collection, statistics and article writing

2. Expected goals

1) The purpose of this study is to clarify the impact of skeletal sarcopenia on the overall survival rate and progression free survival rate of early and mid-term non-small cell lung

cancer, as well as its clinical value in predicting the prognosis of patients.

- 2) The research results will provide high-quality evidence-based medicine evidence for the formulation, revision and optimization of international and domestic lung cancer clinical guidelines and expert consensus, and the research has certain social value.
- 3) While further cultivating the clinical trial research team, the research team will publish at least 2 clinical research papers as the first / corresponding author in the International Journal of respiratory medicine consistent with the funding direction of the project.
- 4) At least one provincial and municipal project in the direction of relevant disciplines of the new project.
- 5) Make special or general assembly speeches at important international conferences in this field.

14、References

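### The plan promises sarcopenia's clinical value as a predictor, but its only survival analysis, Kaplan-Meier with log-rank, cannot show what sarcopenia adds to stage and ECOG

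*Combined protocol and SAP*

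**What the plan says.** The predictive aim appears three times. The last paragraph of the background sets out to "clarify the value of sarcopenia and nutritional status in predicting the overall survival rate and progression-free survival rate". Section 2, purpose 3, names the impact of sarcopenia on OS and PFS and then "its clinical value as a predictor of the prognosis of patients". Section 13, expected goal 1, repeats both parts, ending "as well as its clinical value in predicting the prognosis of patients".

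Section 6 item 5 fixes the endpoint and horizon: "The primary endpoint was progression free survival (PFS) within 2 years" and "The deadline for follow-up is 2 years", with OS secondary. Section 8 item 3, on prognostic value, gives the whole analysis: "progression free survival time PFS and overall survival time OS were statistically analyzed by Kaplan-Meier, and the difference was tested by log-rank method". It names no covariates.

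The one multivariable model is in section 8 item 2: "Logistic regression was used to analyze the risk factors of sarcopenia in non-small cell lung cancer". Its outcome is sarcopenia, not PFS or OS.

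Section 4 admits patients where "the TNM staging diagnosis of lung cancer meets the stage IA-IIIA". Section 6 records age, stage and ECOG. Stage is used in the group description (section 8 item 1) and in the logistic model, but neither stage nor ECOG enters a PFS or OS analysis. The documents mention no Cox model, hazard ratio, C-index, AUC, or comparison with a model based on stage.

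**The concern.** Purpose 3 has two parts. Whether sarcopenia affects survival is a question about a difference between groups, and a log-rank test speaks to it. Clinical value as a predictor also raises two further questions: how well the marker separates patients who progress from those who do not, and whether it tells a clinician anything beyond what stage and performance status already tell. The second question is pressing in a cohort running from IA to IIIA, where stage is an obvious competitor.

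A curve comparison by sarcopenia status alone cannot answer that second question, whatever its p-value. If the analysis stops there, the study reaches its stated goal of informing guidelines without the estimate that this goal needs.

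**Working it through.** **The plan's own figure.** Section 5 gives 66 per group and 132 in total, from a base rate of 25.2%, OR 3.2, alpha 0.05, power 0.80 and missing data below 10%.
- Odds 0.252/0.748 = 0.337; × 3.2 = 1.078; second proportion = 1.078/2.078 = 0.519.
- Two-sided comparison of two proportions with continuity correction: 59 per group. 59/0.9 = 65.6, so 66 per group and 132 in total. The figure reproduces.
- In section 5 the OR describes tumor and sarcopenia, not sarcopenia and PFS. It therefore supplies no PFS effect, and the inputs below are assumptions.

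**Discrimination at 24 months.** Assumed: HR 2.0 and a 2-year event rate p0 without sarcopenia of 10% to 40%. Two splits are used: 66/66 (the 1:1 ratio of section 5) and 57/75 (the 43% prevalence in the background, 0.43 × 132 = 56.8). Status at 24 months is treated as known for everyone.
- p1 = 1 − (1 − p0)^HR
- sensitivity = n1·p1/(n1·p1 + n0·p0)
- specificity = n0(1 − p0)/(n0(1 − p0) + n1(1 − p1))
- AUC of a yes/no marker = (sensitivity + specificity)/2

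| p0 | p1 | 66/66: sens, spec, AUC | 57/75: sens, spec, AUC |
|---|---|---|---|
| 0.10 | 0.19 | 0.66, 0.53, 0.59 | 0.59, 0.59, 0.59 |
| 0.20 | 0.36 | 0.64, 0.56, 0.60 | 0.58, 0.62, 0.60 |
| 0.30 | 0.51 | 0.63, 0.59, 0.61 | 0.56, 0.65, 0.61 |
| 0.40 | 0.64 | 0.62, 0.63, 0.62 | 0.55, 0.69, 0.62 |

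The AUC depends on the split and the risks, not on the total number; the number governs precision.

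**The test can succeed at the same effect.** Take 57/75 and p0 = 0.30. Expected events are 57 × 0.51 + 75 × 0.30 = 51.6. Power = Φ(ln 2 × √(51.6 × 0.432 × 0.568) − 1.96) = Φ(0.51), about 69%, with AUC 0.61. At HR 2.5 power is 93% and AUC 0.65. Working from the test instead, at 66/66 a result just reaching p = 0.05 means HR = exp(1.96 × 2/√events). For 20, 40 and 80 assumed events this is 2.40, 1.86 and 1.55, with AUC 0.61, 0.59 and 0.58.

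**Gain over stage.** This was simulated with sarcopenia HR 2.0 and an assumed stage HR of 1.45 per stage group. One set of runs gave a C-index of about 0.65 to 0.67 for stage alone and a gain of about 0.03. A second set, with five equal stage groups, gave 0.64 and a mean gain of 0.037, or 0.047 among studies with p < 0.05. The range is therefore about 0.03 to 0.05.

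**Precision.** With about 40 events, an AUC of 0.59 has a 95% interval of roughly 0.50 to 0.68. At HR 2.0 and 66/66, expected events run from 66 × (0.10 + 0.19) = 19 to 66 × (0.40 + 0.64) = 69. Four model terms (stage, age, ECOG, sarcopenia, one each) then have about 5 to 17 events per term.

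**The case against.** The case for leaving the plan alone has real substance.

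- **The wording is loose.** Predictor may mean no more than a factor associated with outcome, and the documents promise no risk score or accuracy figure. This stands in part. However, the background describes nutritional score as an independent factor for prognosis, and even that sense calls for adjustment, which item 3 lacks.
- **Discrimination is already obtainable.** A reader might infer that the plan yields no measure of discrimination. It does not report one, but the 24-month Kaplan-Meier estimates and the group sizes give sensitivity, specificity and AUC by the formulas above. This stands, and it makes that half of the matter one of reporting. The gain over stage cannot be recovered in this way.
- **The misuse is hypothetical.** A reader might infer that p < 0.05 will be declared clinical value. No passage says so. The plan sets no criterion for clinical value at all.
- **The remedy overlaps with confounding adjustment.** The same Cox model would serve both purposes. If it is added for that reason, what remains is the comparison with and without sarcopenia.
- **A pass/fail rule would be poor.** It is tempting to allow the claim only if the interval for the gain excludes zero. In rough simulations at HR 2.0, such a rule passed in 42% to 63% of studies with a percentile bootstrap interval and 18% to 22% with a normal-approximation interval. With no true effect, the mean apparent gain was still about 0.01. The rule would depend on the interval method and ignore optimism.

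**Conclusion.** The objective and the analysis do not match: nothing in the plan estimates what sarcopenia adds to stage and ECOG for PFS or OS. At HR 2.0 the 24-month AUC is about 0.59 to 0.62, and the C-index gain over stage is about 0.03 to 0.05. A reader might call that gain very small or take it to show that sarcopenia is useless as a predictor. Neither follows: on a C-index of about 0.64 to 0.67 the gain is modest, and the true effect is unknown.

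The AUC range holds for both splits and for event rates of 10% to 40%. The C-index gain rests on a stage mix and a stage hazard ratio that the documents do not give, so it is less certain. The absence of a comparison with stage rests on the text alone and on none of these assumptions.

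**What to change.** Add to section 8 item 3:

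- A Cox model for PFS, and for OS if events allow, with a small prespecified set (stage, age, ECOG), fitted with and without sarcopenia.
- The adjusted hazard ratio for sarcopenia with its 95% CI.
- The change in C-index or 24-month AUC, with an optimism-corrected bootstrap 95% CI by an interval method named in advance.
- The 24-month PFS by group, with the resulting sensitivity and specificity.

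Keep Kaplan-Meier and log-rank as the group comparison. Report the gain descriptively, with no pass/fail threshold, and base any statement about clinical value as a predictor on these estimates and not on the log-rank p-value alone.

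The cost is about a paragraph of SAP text and no new data, since every variable is already collected. The bootstrap goes beyond the standard menus of the SPSS 24.0 named in section 8, and the interval for the gain will be wide. If this work is not wanted, the alternative is to remove the predictive-value wording from the background, purpose 3 and expected goal 1.

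### The only vital-status contact specified for withdrawn patients is 24 weeks after withdrawal, so for those leaving before about month 18.5 no specified check reaches the 2-year horizon for OS

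*Combined protocol and SAP*

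**What the plan says.** Section 9 (Ethics related to experiment) covers patients who leave. "For all subjects who withdrew from the study for any reason", staff are to "contact themselves or their families or health care providers 24 weeks after withdrawal to determine the subject's life status". That is one time point, counted from withdrawal. No other section sets a later vital-status check for these patients.

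Exclusion criterion 6 in section 4 makes the group wider than those who refuse: it treats any loss to follow-up, whatever the cause, as withdrawal. It also places withdrawal among the exclusions.

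Section 6, item 5 (Follow up endpoint) sets the horizon: "The deadline for follow-up is 2 years". Under the primary endpoint, PFS within 2 years, deaths of every cause count as events. OS, the secondary endpoint, also starts at diagnosis and counts all deaths. Assessments are "at 6, 12, 18 and 24 months after enrollment", and "If feasible, the participants will continue to be followed up for up to five years".

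Section 8, item 3 plans Kaplan-Meier curves and a log-rank test for PFS and OS and gives no censoring rule for withdrawals. Section 11 plans a closing round: "From November 2023 to January 2024, the final follow-up was completed and the outcome events were collected and sorted out".

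**The concern.** The contact is tied to the date of withdrawal, whereas the endpoint is tied to a fixed 2-year horizon. The earlier a patient leaves, the more of the window passes after the last specified check. If nothing else is done, OS for that patient is censored at about 5.5 months after withdrawal, and a later death within the 2 years is not sought.

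Kaplan-Meier and log-rank rely on censoring being unrelated to prognosis within each group. Here it may not be: the study requires grip and walking tests every six months, and the background section links muscle loss to progressive functional decline, so patients who stop attending may differ from those who stay. At stake is the OS part of research purpose 3, the effect of sarcopenia on survival, in a cohort planned at only about 132. An analysis rule can be repaired later; vital status that was never collected may not be recoverable.

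**Working it through.** **Inputs.** Contact at 24 weeks after withdrawal (section 9); horizon 24 months (section 6, item 5); cohort of 132 and an allowance of up to 10% for incomplete data (section 5). The documents give no death rate and no expected number of withdrawals.

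**The plan's own figure.** The cohort size enters only the illustration, but it can be reproduced. With p1 = 0.252 and OR 3.2, the odds are 3.2 × 0.252 / 0.748 = 1.078, so p2 = 1.078 / 2.078 = 0.519. A two-sided 5% test at 80% power with continuity correction needs 59 per group; 59 / 0.9 = 65.6, or 66 per group and 132 in total. This agrees with section 5. The timing gap does not depend on it.

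**Cut-off.** 24 weeks = 168 days; 168 / 30.44 = 5.52 months. A contact reaches month 24 only if withdrawal is at or after 24 − 5.52 = 18.48 months.

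**Gap by month of withdrawal m**, gap = max(0, 24 − m − 5.52):

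| Withdrawal (month) | Status sought up to (month) | Months of the 2 years left uncovered |
|---|---|---|
| 3 | 8.5 | 15.5 |
| 6 | 11.5 | 12.5 |
| 12 | 17.5 | 6.5 |
| 18 | 23.5 | 0.5 |
| 18.5 or later | 24 or later | 0 |

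**Which clock.** Month 18.5 is on whichever clock the 2 years use. Visits count from enrollment, while PFS and OS count from diagnosis. If the 2 years also run from diagnosis, the cut-off is 18.5 months after diagnosis, which is earlier on the enrollment clock.

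**Share of deaths after the contact (assumed constant hazard).** With two-year mortality q, λ = −ln(1 − q) / 24, and the share of deaths between withdrawal and month 24 that fall after the contact is 1 − [1 − exp(−5.52λ)] / [1 − exp(−(24 − m)λ)]. For q = 20% and m = 6: λ = 0.2231 / 24 = 0.00930, and the share is 1 − 0.0500 / 0.1541 = 0.675. Over q = 10% to 30% the share is 71-73% at month 3, 66-69% at month 6, 52-53% at month 12 and 37-38% at month 15. It is zero from month 18.5. One half is therefore a middling assumption for a mix of withdrawal times.

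**Illustration of size (all rates assumed).** Withdrawals: 10% of 132, about 13. Deaths in the cohort: 10-20% of 132, about 13-26. Half of the withdrawals' deaths come after the contact.

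- Withdrawals die at the cohort rate: 13 × 0.10 × 0.5 = 0.65 of 13 deaths, or 13 × 0.20 × 0.5 = 1.3 of 26 deaths; 5% in both cases.
- 30% of withdrawals die: 13 × 0.30 × 0.5 = 1.95, about 2 deaths; 2 / 26 = 8% and 2 / 13 = 15%.

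The 15% end is extreme: it puts 13 × 0.30 = 3.9 of 13 deaths, or 30%, in about 10% of the patients.

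**The case against.** Several stronger readings are tempting, and the documents do not support them.

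- **That later deaths are certain to be missed.** Section 9 names one time point but does not say it is the only contact. Section 6, item 5 describes follow-up through clinic and electronic records and by telephone, and the closing round in section 11 is not expressly limited to patients still in the study. The documents do not say whether either continues after withdrawal. What can be said is that no later check is specified.
- **That the primary endpoint is seriously damaged.** Death counts in PFS, but progression must be confirmed by imaging and a clinical expert. A vital-status call supplies neither, and a death after an unseen progression is not the PFS event. The gain is essentially to OS.
- **That the OS comparison is biased toward no difference.** Censored patients leave the risk set; they are not counted as survivors. Bias needs a later hazard that differs, within a group, between patients who left and patients who stayed. More withdrawal by weaker patients with sarcopenia is plausible but is conjecture, and exclusion criterion 4 already keeps out those who cannot do the walking test.
- **That 8-15% is an estimate.** It rests on an assumed 30% mortality among withdrawals. The 10% in section 5 is a ceiling on incomplete data, not a forecast of withdrawals.
- **That permission for later contact already exists.** The plan provides for contact at 24 weeks; the consent pages are not available to check.

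The strongest objection concerns exclusion criterion 6. Applied as written, it may drop withdrawn patients from the analysis, and then vital status at week 24 or month 24 is equally unused. This stands, and is a larger matter than the timing. It does not remove the point: section 9 collects vital status for these patients, and if they are kept, no check beyond 24 weeks is specified.

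**Conclusion.** The point holds as a gap in specified follow-up, and correcting it is a cheap improvement. For patients who withdraw or are lost before about month 18.5, no check is specified that reaches the 2-year horizon, and the uncovered time is 15.5, 12.5 or 6.5 months for withdrawal at month 3, 6 or 12. That arithmetic is firm, subject only to the choice of clock. The consequence is mainly for OS. If withdrawal is related to prognosis, censoring at the 24-week contact is informative; its direction and size cannot be computed from the documents. On the assumed rates, about 1 to 2 deaths are affected. The benefit of a later check depends on withdrawn patients being retained in the OS analysis.

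**What to change.** 1. In section 9, keep the 24-week contact and add a vital-status contact or record check, noting status and date, at month 24 or in the November 2023 to January 2024 final follow-up. Apply it to every withdrawn or lost patient who has not refused further contact. With enrolment in October to November 2021, month 24 falls at or just before that round, so the calls can be made together.
2. Add a matching line to the consent form.
3. In section 8, state that OS is censored at the last date known alive, and say from which date the 2 years run.
4. Reconcile exclusion criterion 6 in section 4 with section 9, so that enrolled patients who later withdraw stay in the OS analysis. Without this the added data would not be used.

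Cost: one further call or record check per withdrawn patient, about 13 on the assumption above, and the consent line. Some families will be harder to reach at the later date, which is a reason to keep the 24-week contact. The change will not recover missed progression.

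### The only follow-up stated for withdrawn and lost patients asks for life status; the plan does not say that progression, a component of the primary PFS endpoint, is sought after withdrawal

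*Combined protocol and SAP*

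**What the plan says.** - **Primary endpoint (Section 6, item 5).** "The primary endpoint was progression free survival (PFS) within 2 years". Its clock starts at diagnosis, and either recorded progression or death from whatever cause is an event. OS is secondary. Disease evaluation is at 6, 12, 18 and 24 months after enrolment, and for progression "The progress needs to be confirmed by at least one imaging and one clinical expert".
- **Sources of follow-up (same item).** "The patients were followed up according to the outpatient and electronic medical records and telephone calls". The text does not say whether this continues after a patient withdraws.
- **After withdrawal (Section 9).** "For all subjects who withdrew from the study for any reason", staff are to "contact themselves or their families or health care providers 24 weeks after withdrawal to determine the subject's life status". The same section says that stopping participation does not affect further treatment.
- **Who counts as withdrawn (Section 4, exclusion item 6).** Besides those who leave by choice, the item covers patients "regardless of the patient's loss of follow-up caused by any reason, shall be regarded as patients who withdraw from the study". Item (2) of the same list is "Incomplete clinical and follow-up data or disagreement or inability to conduct regular follow -up CT imaging evaluation".
- **Analysis (Section 8, item 3).** PFS and OS by Kaplan-Meier, compared by log-rank. No censoring rule is given for withdrawn or lost patients.

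**The concern.** The one rule written for patients who leave names only one of the two components of the primary endpoint. Staff who follow it to the letter learn whether the patient is alive and nothing about the tumour. A patient who withdraws, progresses in week 8 and is alive in week 24 then contributes no PFS event.

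Kaplan-Meier and log-rank assume that patients censored at a given time have the same outlook as those still followed. In a lung cancer cohort whose exposure is a marker of frailty, withdrawal may well be linked to worsening disease, and perhaps to sarcopenia. In that case the PFS curves are too high, and the group comparison may be distorted.

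The missing information is largely within reach: health care providers are already among the contacts, progression is already taken from records, and usual treatment continues after withdrawal.

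**Working it through.** **The plan's own figure.** Section 5 gives 66 per group and 132 in all. With 25.2% as reference and OR 3.2, the second proportion is 3.2×0.252 / (1 − 0.252 + 3.2×0.252) = 0.8064/1.5544 = 0.519. A two-sided 5% test with 80% power and continuity correction needs 59 per group; 59/0.9 = 65.6, rounded up to 66, so 132. The figure reproduces and this point does not change it. It is not built on PFS, so the documents give neither an expected PFS rate nor an event count. Everything below is illustration under stated assumptions.

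**Assumptions.** Exponential times; 24-month PFS of 65% at the in-study hazard; withdrawal probability d by month 24 of 10% or 20% (Section 5 allows for missing data below 10%; 20% is a stress case); hazard multiplied by m = 3 or 4 after leaving.

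**One-group calculation.** In-study hazard λ = −ln(0.65)/24 = 0.01795 per month. Withdrawal hazard w = −ln(1 − d)/24 = 0.00439 (10%) or 0.00930 (20%).

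True S(24) = exp(−24(λ+w)) + w·exp(−24mλ)·[1 − exp(−24a)]/a, with a = λ + w − mλ. The first term is patients still in the study and event-free; the second is those who left and are event-free.

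Kaplan-Meier censored at withdrawal sees only the in-study hazard and so estimates exp(−24λ) = 0.650 in every row.

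| d | m | True S(24) | Kaplan-Meier | Overstatement |
|---|---|---|---|---|
| 10% | 3 | 0.5850 + 0.0432 = 0.628 | 0.650 | 2.2 points |
| 10% | 4 | 0.5850 + 0.0361 = 0.621 | 0.650 | 2.9 points |
| 20% | 3 | 0.5200 + 0.0858 = 0.606 | 0.650 | 4.4 points |
| 20% | 4 | 0.5200 + 0.0713 = 0.591 | 0.650 | 5.9 points |

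With m = 1 the formula returns 0.650: no bias. In simulation (400,000 patients per row), adding events from the 24 weeks after withdrawal gives 0.62 to 0.64 and removes about half the bias.

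**Events recovered.** 10% of 132 is 13 withdrawals; 24 weeks is 24×7/30.44 = 5.5 months. Expected progressions are 13×[1 − exp(−5.5mλ)]. Over 24-month PFS of 60% to 80% and m from 1 to 4 this runs from 0.7 to 4.9, so about 1 to 5. In-study PFS of 60% to 80% would mean about 132×0.2 = 26 to 132×0.4 = 53 events in all. The 1 to 5 is an upper bound, because it assumes every withdrawn patient is traced.

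**Two-group calculation.** Assume in-study 24-month PFS of 75% without sarcopenia and HR 2, so 0.75² = 56.25% with it. Censoring at withdrawal shows 75 − 56.25 = 18.75 points whatever the withdrawal rates. The true difference applies the formula above to each group:

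| Withdrawal without / with sarcopenia | True difference (m = 3 to 4) | Loss from censoring |
|---|---|---|
| 10% / 10% | 19.2 points | 0.5 |
| 20% / 20% | 19.7 points | about 1 |
| 5% / 15% | 21.3 to 22.0 points | 2.6 to 3.3 |
| 10% / 20% | 21.6 to 22.3 points | 2.9 to 3.5 |

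In the last row, capturing progression at 24 weeks brings the shown difference to about 20.3 to 21.0 points. With equal withdrawal the hazard ratio does not shrink at all: censoring shows 2.00 against a true ratio of cumulative hazards of about 1.92 to 1.98.

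**The case against.** **Progression may still be followed through records.** Section 6 describes follow-up by outpatient and electronic records and by telephone, and nothing ends it at withdrawal. The Section 9 contact sits in the ethics text and may be meant as a minimum check. This stands in part. A reader might infer that progression is never sought after a patient leaves; the documents do not say so, and that would be a reading from silence. They support only that no section states it and that the one rule specific to these patients stops at life status.

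**The endpoint is not shown to be one-sided.** A reader might also infer that deaths after withdrawal enter PFS while progressions do not. The plan never says how the 24-week life status is used, so unequal ascertainment follows only if those deaths are counted.

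**The group difference need not shrink.** This is right. Attenuation needs both a worse prognosis after leaving and clearly unequal withdrawal, and the documents give evidence for neither. The 6-point figure likewise needs 20% withdrawal and a 4-fold hazard, neither of which comes from the plan.

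**These patients may not be in the analysis at all.** Items (2) and (6) of Section 4 list incomplete follow-up, withdrawal and loss as exclusions, although these are events after enrolment. Read literally, they remove such patients, and a better contact would then recover nothing. This does not defeat the point, but the fix has to settle it.

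**Conclusion.** The point holds as a gap in a stated rule: life status is the only information that the plan says it will seek from withdrawn and lost patients, and progression is a component of its primary endpoint. The size is modest. Under the assumed 65% PFS and 3- to 4-fold hazard after leaving, 24-month PFS is overstated by about 2 to 3 points at 10% withdrawal and by up to 6 at 20%. The sarcopenia difference loses about 2.5 to 3.5 points when withdrawal is about 10 percentage points more common with sarcopenia, and about 0.5 to 1 point when it is equal. If leaving is unrelated to prognosis there is no bias, only a few missed events. The change is worth making because it is cheap and bears on the primary endpoint, not because the study's conclusion is shown to be at risk.

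**What to change.** 1. **Section 9.** Extend the planned contact. Where the patient has not refused further data collection, ask for life status and date of death. From the health care provider or hospital record, obtain whether and on what date progression as defined in Section 6, item 5 was recorded, and the date of the last imaging.
2. **Section 4.** State that enrolled patients who later withdraw, are lost or have incomplete follow-up stay in the PFS analysis and are not excluded under items (2) and (6).
3. **Section 8, item 3.** State the rule: progression counts on its recorded date; death from any cause counts on its date; patients with neither are censored at the last imaging without progression.

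**Cost.** A few more questions at a contact already planned, a record look-up, and a check that the consent covers it (the consent pages are not in the copy reviewed). Sample size, visits and treatment are unchanged.

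**Limits.** Some dates will come from imaging done elsewhere, and not all lost patients will be traced. A single contact at 24 weeks does not reach month 24 for early leavers: someone who leaves at month 3 is contacted at about month 3 + 5.5 = 8.5, which leaves some 15 months unobserved.
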